## 5 Data Analysis

Describe the data analysis plan, including any statistical procedures or power analysis.

The data will be randomly assigned with serial ID numbers. All tests will be assumed two-sided and an alpha level of .05 will be used. SAS 9.4 will be used for data processing and all statistical analyses. Missing data will be handled by multiple imputations of dependent values. 101–103 Analyses just of complete data will be conducted and comparisons of groups with and without missing data will be made. In addition, sensitivity analyses of complete data will be conducted and compared imputed data analysis. An **intent-to-treat** analysis will be employed. For **Hypotheses 1 to 3**, differences in continuous outcome measures over time will be examined using **linear mixed-effects modeling.** In particular, we will fit mixed effects models to each continuous outcome measure. We will use random intercepts as well as explore random slopes to represent subject level variability. Fixed-effects corresponding to group, time and group x time interaction will be included in the model. A significant group x time interaction will indicate substantial differences in the groups over time. Restricted maximum likelihood method will be used for estimation, and the most appropriate covariance structure will be examined.

Since Data and Safety Monitoring Boards (DSMBs) are required only for phase III clinical trials (NOT-OD-00-038.html), we do not include a DSMB for this intervention study. For the proposed intervention study, we have

the following data safety monitoring plan (DSMP). First, to manage and protect the data collected, only summary data will be openly accessible to funding agency or will appear in publications. Research participants will be informed that they are free to decline to answer any questions they do not wish to answer or to stop participating in the project at any time. When a participant withdraws from participation, the data that they have provided will be immediately removed. Also, the data will have no identifying information to link a subject to the data.

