## **35** Early Withdrawal

Only complete this section if there are planned conditions under which a participant will be withdrawn from the study. If not applicable, skip to next section. Include this information in your consent form.

A List the criteria for withdrawing individual participants from the study (e.g., safety or toxicity concerns, emotional distress, inability to comply with the protocol, or requirements from study sponsor).

To input text, click in the light grey area below.

While the participants fill out the questionnaire, several random questions that they have already answered will be repeated to check consistency for the purpose of **identity and authenticity verification**. When inconsistency is detected, the participant will not be allowed to continue her participation in the study. This mechanism has been used in the former studies of the PIs without a problem.

The participants have the right to leave a study at any time without penalty. If they want to withdraw, they need to send an email notification or a text message indicating their withdrawal to the research team. Participation is voluntary, refusal to participate will involve no penalty or loss of benefits to which the subject is otherwise entitled, and the subject may discontinue participation at any time without penalty or loss of benefits to which the subject is otherwise

entitled. New findings developed during the course of the research that may affect the subject's willingness to continue to participate will be provided to the subject.

B Describe any necessary procedures for ensuring the safety of a participant who has withdrawn early.

To input text, click in the light grey area below.

Those who withdraw will be encouraged to seek mental health help if and when necessary, but no further actions from the research team after they withdraw.

Describe any pre-specified criteria for stopping or changing the study protocol due to safety concerns.

To input text, click in the light grey area below.

None specific for this study. The study will follow the NIH policies and regulations.

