#### PRIVACY AND CONFIDENTIALITY

#### 38 Privacy

Describe how you will protect the identity and privacy of study participants during each phase of research. Privacy focuses on the individual participants rather than data. In this section, researchers should focus on issues such as where research activities take place and how participant involvement is protected from non-participants. Describe methods to ensure participants' privacy during identification, recruitment, screening, the consent process, the conduct of the study, and dissemination of data.

To input text, click in the light grey area below.

All the procedures will happen at the project server and website. The participants will use pseudonym during their participation in the intervention components through the project website; research staff members or other participants will not be able to identify them. Also, the participants will join the study independently through the project website, so non-participants will not know that they join the study.

To manage and protect the data collected, only summary data will be openly accessible to funding agencies or will appear in publications. Research participants will be informed that they are free to decline to answer any questions they do not wish to answer or to stop participating in the project at any time. When a participant withdraws, the data that they have provided will be removed immediately. Also, the data will have no identifying information to link a subject to it. The collected data will be recorded in a database using postgreSQL. The database backup will be performed daily and will be encrypted. Again, data in the servers will be daily monitored by the engineering PI, [name], to ensure its safety and security.

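### Sections 5 and 38 order removal of a withdrawing woman's data, so her completed questionnaires cannot inform the intent-to-treat and missing-data analyses that section 5 promises

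*Combined protocol and SAP*

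**What the plan says.** Section 5 (Data Analysis) sets out the analysis in these terms: "An intent-to-treat analysis will be employed"; "Missing data will be handled by multiple imputations of dependent values"; "comparisons of groups with and without missing data will be made"; "sensitivity analyses of complete data will be conducted and compared imputed data analysis". Inference rests on a mixed model for each continuous outcome: "A significant group x time interaction will indicate substantial differences in the groups over time".

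Later in section 5, in the data safety monitoring plan, comes the rule: "When a participant withdraws from participation, the data that they have provided will be immediately removed". Section 38 (Privacy) repeats it: "When a participant withdraws, the data that they have provided will be removed immediately". Neither place makes an exception for questionnaires already completed.

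Section 35 (Early Withdrawal) makes withdrawal an active step; women who want to leave are told that "they need to send an email notification or a text message indicating their withdrawal to the research team". In the Procedure Description (Phase 2), eligible women are randomised and then asked for the baseline questionnaire. The proration schedule in section 45 describes payment to women who withdraw after the pre-test and after the 1-month test.

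**The concern.** Intent-to-treat means analysing women as randomised and using what was observed on them. Imputation and mixed models draw on a leaver's earlier answers to represent her later ones. A rule that erases those answers on withdrawal takes away that information for exactly the women on whom these methods depend.

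The planned check of imputed against complete-data results cannot show the effect, because her answers are in neither dataset. Deleted questionnaires also cannot be recovered at analysis, so the matter has to be settled before withdrawals occur. At stake are the group x time contrasts, on which Hypotheses 1 to 3 are judged, and the accuracy of calling the analysis intent-to-treat.

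**Working it through.** **1. The texts side by side.**
- Who is affected: a woman who is randomised, has at least one questionnaire on file and sends an email or text notice. The Procedure Description and section 45 show that the plan foresees such women.
- What is removed: the data she has provided, which on plain reading means her questionnaires.
- What may survive: arm assignment comes from the website's random number generator (section 17), and usage logs are recorded by the server (Procedure Description). The removal rule does not clearly cover either.
- Consequence: her answers cannot enter the mixed model or inform imputation. If arm assignment survives, she can be listed as randomised with all outcomes missing. Any imputation would then rest on little more than her arm, which is nearly uninformative.
- Reconciling text: none found. No modified analysis set is defined, and no provision keeps data collected before withdrawal.

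**2. Possible size of the bias.** The plan has no figure to reproduce here, because it states no withdrawal rate. From section 15: 30 women per group. Assumed: no true effect; outcome SD 1, higher = worse; equal correlation ρ = 0.6 between visits; withdrawal after month 1 in one arm only at rate r; probability of leaving p logistic in a driver S, with slope 1 per outcome SD.

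Under deletion only stayers are analysed, so for change D from baseline

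bias = −Cov(D, p) / (1 − r) = −Cov(D, S) × E[p(1 − p)] / (1 − r),

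where the second step holds for jointly normal D and S. Numerical integration at r = 0.20 gives E[p(1 − p)] = 0.142 when S is the month-1 change and 0.139 when S is a single-visit level. The covariances follow from ρ: 2(1 − ρ) = 0.8, 1 − ρ = 0.4, or 0.

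| Leaving depends on | Month 1 | Month 3 |
|---|---|---|
| Worsening by month 1 | −0.8 × 0.142 / 0.8 = −0.14 | −0.4 × 0.142 / 0.8 = −0.07 |
| Month-1 level | −0.4 × 0.139 / 0.8 = −0.07 | 0.00 |
| Baseline level | +0.4 × 0.139 / 0.8 = +0.07 | +0.07 |
| Nothing related to outcome | 0.00 | 0.00 |

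Units are outcome SDs; negative favours the arm that loses women. For ρ from 0.4 to 0.8 the first row runs from −0.20 / −0.10 to −0.08 / −0.04. At 10% v 0% it is −0.07 / −0.04, about half. Equal withdrawal by the same mechanism in both arms gives about zero.

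For scale, the standard error of the month-1 contrast at 30 per arm is √(2 × 0.8 / 30) = 0.23 SD.

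**3. What keeping the data achieves (20% v 0%, ρ = 0.6).** In a large-sample simulation, month 3 was regressed on the kept baseline and month-1 values.
- If leaving depends on baseline or month-1 values, or on nothing, the bias is about zero. This is the missing-at-random case.
- If leaving depends on the unseen month-3 level, month-3 bias is 0.10 SD kept v 0.07 SD deleted.
- If leaving depends on change from baseline to month 3, it is 0.10 SD kept v 0.14 SD deleted.
- The month-1 contrast stays unbiased in all these cases, because every month-1 answer is still on file.

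**4. Precision, 20% loss in each arm.** The detectable difference at 80% power and two-sided .05, in SDs of change, is (1.960 + 0.842) × √(2 / n).
- No loss, n = 30: 0.72.
- Deleted, n = 24: 0.81 at both times.
- Kept: 0.72 at month 1. At month 3, the variance of change (0.8) splits into 0.55 not predicted by the first two visits and 0.25 predicted. The result is 2.802 × √(2 × (0.55/24 + 0.25/30) / 0.8) = 0.78.

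**The case against.** Four arguments carry weight.

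*The rules do not strictly exclude each other.* A reader might infer that both cannot be followed, and that a withdrawer falls in neither missing-data comparison group. The documents do not support that. If arm assignment survives, she can be counted as randomised and placed with the women who have missing data. What stands is narrower: her answers are lost to every analysis.

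*Keeping data is not a cure.* A reader might infer that retention removes the bias. It does so only when leaving depends on values already observed. If leaving depends on unseen month-3 values, month-3 bias remains and can exceed that under deletion. Retention still preserves the month-1 data and their precision.

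*The reach is limited.* The rule needs active notice, the withdrawal rate is unknown, and the biases are small beside a standard error of 0.23 SD. A woman who leaves before month 1 loses only her baseline answers. The study is a 60-woman pilot that section 15 calls explorative. This lowers the severity but does not reconcile the text.

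*Deletion protects participants.* That is a legitimate choice. It calls for deletion on request, or for an honest label on the analysis; it does not justify an unqualified intent-to-treat claim. The consent pages are not available, so what women were promised is unknown.

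**Conclusion.** The plan is wrong as written and should be corrected, though this is not a critical fault. Sections 5 and 38 remove the questionnaires of randomised women who formally withdraw, while section 5 promises analyses that need those questionnaires. This conclusion rests on the text alone.

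The size is conditional on assumed rates and mechanisms. At 20% v 0% withdrawal after month 1 and correlation 0.6, the bias is about 0.14 / 0.07 SD (months 1 / 3) for leaving on worsening and 0.07 / 0.00 SD for leaving by month-1 level. The sign reverses for leaving by baseline level, and the bias is zero for leaving unrelated to outcome. The documents do not support a claim that the trial's result will be biased in a known direction or by a known amount.

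**What to change.** Replace both removal sentences (sections 5 and 38) with:

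> On withdrawal, new data collection stops; data already provided are retained under the serial ID and analysed as randomised unless the participant asks for deletion; withdrawals and deletions are counted and reported by arm.

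Apply this prospectively, with a matching consent sentence through an IRB modification, and honour any deletion promise already made.

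State how a withdrawal notice is matched to a serial ID. Sections 5 and 38 say the data carry no identifying link, and section 41 says email addresses are not linked to the data. Deletion on withdrawal needs the same match, so the present rule leaves this open too.

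If automatic deletion is kept, section 5 should not call the analysis intent-to-treat without qualification, and deletions should be reported by arm.

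Cost: two sentences, a count by arm, one consent sentence, a description of the ID match and one IRB modification. The downside is that deletion becomes on request rather than automatic, and some informative loss can still occur through such requests.

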#### STUDY ELEMENT IDENTIFICATION

## 6 Study Elements

Check each research procedure included in your study.

A full description of all study procedures should be provided in the Procedures (Details) section below. Procedures denoted with "\*" below have supplemental forms. Navigate to the UTRMS-IRB Library, Templates tab to download the applicable supplemental form.

Bio-specimens*	Biometrics	Registry or Repository*
Focus Group	Genetic Analysis	Genomic Data Sharing
International Research*	Interview/Survey	MRI
Protected Health Information*	Observation	Radioactive Material/PET/Nuc. Med
Record Review	Sensors (Externally Placed)	Sensors (Inserted)
Audio (only) Recording	Video Recording	X-Ray/CT/DEXA

## 7 Study Intervention

Click on the check box (or double click and type an "X" if using Google Docs) if you will implement any of the following interventions.

A full description of all study interventions should be provided in the Procedures (Details) section below.

	Tem	plates tab to download the applicable supplemental form.
		Behavioral Device* Drug/Biologic*
8	Cli	nical Trial
	Click	on the following check box (or double click and type an "X" if using Google Docs) if the research meets the w definition of a clinical trial.
		This study meets the definition of a clinical trial according to clinical trials.gov in that it involves one or more human subjects who are prospectively assigned to one or more interventions (which may include placebo or other control) to evaluate the effects of those interventions on health-related biomedical or behavioral outcomes.
9	Chec	ditional Oversight  the box(es) below if you are implementing research procedures that require oversight from additional UT mittees.
		Energy introduced to the subject human induced (electrical, magnetic, light)
		Biological Samples, Biohazards, Recombinant DNA, or Gene Transfer
		If biological samples are used and stored on UT campus UT IBC approval is needed.
	a	UT IBC has (or will have) oversight.
		Provide UT IBC Number:
	b	Biological samples collected will not be stored at UT Austin and another
		agency has responsibility for biospecimen safety.

\* Interventions denoted with "\*" below have supplemental forms. Navigate to the UTRMS-IRB Library,

## **10** Alternatives to Participation in This Study

Provide a description of alternatives to participation in this study, as applicable.

Since this is not a treatment study, the alternative is not to participate.

#### STUDY PROCEDURE DESCRIPTION

# Procedure Description

1

Describe all study procedures, including a step-by-step outline of what participants will be asked to do or how data will be used. Be sure to describe all of the following in detail, as applicable:

- Description of all research procedures being performed and when they are performed, in sequential order.
- Describe/list all research measures/tests that will be used [NOTE: upload copies of all measures, surveys, scripts, data collection forms, etc., in "Other Attachments" in UTRMS-IRB].
- Secondary data or specimens that will be obtained, how they are collected, how are they used.
- Where research activities will take place and duration (include expected time commitment of participants).
- Study elements checked in #6 above should be described here.

*Note: if this is a multi-site or collaborative study include the following:* 

- This is a "Multi-site Study that involves more than one site performing ALL aspects of the research procedures as outlined above." OR "This is a collaborative study that involves UT Austin researchers working with external researchers who are engaged in performing the following study activities (list activities)."
- For assistance with multi-site/collaborative research, download HRP-UT932 Request to Rely Assessment Form from the UTRMS-IRB Library and email [contact].

The study includes two phases: (a) Phase 1 including an expert review and a usability test and (b) Phase 2 (a randomized control trial among 60 AACA). Only Phase 2 will be conducted at the Univ. of Texas at Austin.

#### Phase 1 (Aim 1)

For the expert review, the Cognitive Walkthrough method,  will be used with several topics related to the logistics and content of TACAD (including the adequacy of cultural tailoring and specific unique needs of Asian Americans). Please see the below for the details on TACAD. First, 5 self-identified experts in family caregivers of PLAD who never participated in any previous studies of Pls will be recruited through announcing the study at and outside Emory University, and asked to provide their evaluation on the TACAD within 2 weeks. Five experts are an adequate number for an expert review.  For a usability test, the first 10 AACA who agree to evaluate an early version of the TACAD, will be involved in a 1-month-long online forum. On the forum site, 1-2 topics related to specific areas for which the users' evaluation is needed will be posted each week. The topics include: (a) the overall structure, (b) preferences for color, designs, and menus, (c) preferences for content, (d) technical support and difficulties, (e) areas for additional content, (f) preferences for Internet resources, and (g) other issues (the adequacy of cultural tailoring and specific unique needs of Asian Americans). The messages will be analyzed using

a content analysis.  About 80-90% of usability problems could be identified by about 5-10 participants.  The findings from Phase 1 was incorporated into the refinement of TACAD.

Phase 1 was completed at Emory and TACAD was defined based on the findings. Thus, the data from the first phase will not be shared with UT research team.

#### Phase 2 (Aim 2)

All research activities in Phase 2 will be done virtually. The study website will be developed first. The study website is the Web-App of the intervention program. The website at Emory was originally developed and refined by the other PI, [name], and it is owned by [name]. As soon as the grant transfer is completed, the website will be housed at The Univ. of Texas at Austin. To access/use the program through the website, the participants will be provided with an account with ID and passwords, which they could change at their convenience. The data collected through the website will be just the data on the participants' activities in the website (e.g., how many times per week they log in and out, what components they used in the website, how many messages that they are posting) that will be used to determine the dose-response effect of the program later. The current website at Emory is: https://tacad.nursing.emory.edu Again, the website will be moved to UT- Austin once the grant transfer is completed, which requires this IRB approval.

When potential participants visit the website, they will review the "informed consent" and click "I agree to participate" if they agree. After checking them against the inclusion criteria, only those who meet the criteria will be automatically **randomized** into two groups within each sub-ethnic group using an automated random number generator through the website. The randomization will be done within each sub-ethnic group to have an adequate number of participants in each sub-ethnic group. The intervention group (Group 1) will use both TACAD and Alzheimer's Association (AA) website while the control group (Group 2) will use only AA website. The women will be asked to fill out the baseline questionnaire. Then, they will be provided with IDs and passwords to log on the website. Both groups will have an electronic instruction sheet on when they need to come back and fill out questionnaires (see the below for the instruments) and/or use TACAD (see the below for more information on TACAD). Also, both groups will use the AA website (see the below for more information on the website) for 3 months. Only the intervention group will use TACAD for 3 months. Basically, they need to use TACAD and/or the AA website whenever they want to use; no requirement for reimbursement. They are recommended to visit the

months. Only the intervention group will use TACAD for **3 months**. Basically, they need to use TACAD and/or the AA website whenever they want to use; no requirement for reimbursement. They are recommended to visit the project website at least once a week and the intervention group is recommended to have weekly coaching/support sessions with the interventionists through chatting. At first time of use, the participants will have an informational session on the proper use of AA website and TACAD (with instructions on headsets) by phone and/or a webcam. During the intervention, the participants will provide their feedback on the research process as well as TACAD. Two weeks before the end of the 1st and the 3rd months, both groups will fill out the next set of the instruments; it usually takes about 30 minutes to complete each questionnaire. The questionnaires will be provided via **Qualtrics**. In addition, during the intervention period, the participants will be screened using the PHQ-9 only if the research team identifies severe depressive symptoms or suicidal ideation at any time point. We will make immediate recommendations for psychiatric referral for those with scores more than 10 on the PHQ-9 (the cut-point of moderate depressive symptoms; range=0~27) as the literature suggestsIn such cases, participants will also be dismissed from the study.

TACAD. TACAD has four components in three languages (English, Mandarin Chinese, and Korean): (a) 2 sub-ethnic specific social media sites; (b) interactive online educational modules; (c) online resources; and (d) a 360 degree video clipping (a replacement of the VR component that was originally planned). The original VR that we planned to use was discontinued by the developer and only a 360 degree video clipping of the VR component is currently available. Thus, the VR component was replaced with the 360 degree video clipping of the VR. Two languages other than English were adopted because they are the primary languages of Chinese Americans or Korean Americans. The comparability of different language versions has been ensured through the standard-back

translation process. The social media sites will be assisted, coached/moderated, and monitored by culturally matched bilingual RNs under the supervision by PIs. Coaching/support through social mediate sites (with chat functions) will focus on: (a) changing attitudes toward and beliefs about AD and caregiving, (b) building selfefficacy for caregiving, (c) minimizing information needs and uncertainty, and (d) enhancing social support through multiple ways. Within the project website, a social media site (like Facebook) is included. The site is developed by [name] and owned by him. The participants' activities are daily monitored by the interventionists and [name] to prevent any possible harmful effects. The RNs will be trained by the PI. Her/his first 10 messages through social media sites and chat functions will be monitored/evaluated by the research team, and the team's feedback will be incorporated into her/his subsequent interactions. The social media site will be very similar to Facebook. All participants can post their messages (e.g., sharing their experience) and pictures and they can see others' postings. The participants will use their pseudonyms that they choose when they join the study, but their profile pictures will not be posted. All postings will be visible only at the project website. No identifiers will be used except pseudonyms. We also developed online educational modules while considering the women's cultural attitudes found in the literature: TACAD aims to correct misinformation on AD and caregiving by providing stateof-science evidence-based educational content and to provide examples of culturally appropriate caregiving strategies that can be easily adopted. Culturally relevant content (e.g., filial piety, respect for elderly, mind-body interactions, etc.) and culturally tailored educational materials and online resources from Asian scientific authorities are also incorporated. Again, 360 degree video clipping components based on "A Walk Through Dementia (WTD)" will be used to help caregivers learn more about the challenges their loved ones with dementia face, and to build empathy among the caregivers (subsequently changing their attitudes). WTD uses VR technology to give an idea of the challenges faced by people with dementia. Using 3 everyday scenarios (at the supermarket, on the road and at home), users are given insight into some of the symptoms that people with different forms of dementia including AD may experience. The original VR that we planned to use was discontinued by the developer and only 360 degree video clippings of the VR component is currently available. Thus, the VR component was replaced with the 360 degree video clippings of the VR. The 360 degree video clippings basically have the same content of the VR component without the 3-dimentionality, which could be just viewed through Youtube site without any device. They are:

A Walk Through Dementia - walking home (3 minutes 20 seconds) https://www.youtube.com/watch?v=R-Rcbj qR4g&ab channel=AlzheimersResearchUK).

A Walk Through Dementia - at the supermarket (4 minutes 52 seconds) https://www.youtube.com/watch?v=TaeNgo8bR2k&ab\_channel=AlzheimersResearchUK

A Walk Through Dementia - at home (2 minutes 34 seconds) https://www.youtube.com/watch?v=2EO7Dh3fM7Y&ab channel=AlzheimersResearchUK

TACAD also has self-adaptation functionality based on Genetic Algorithm such that the program can deliver the most relevant and effective educational modules and online resources to each participant by using a machine learning method. Cultural tailoring was theoretically guided by the criteria for rigor in cross-cultural research. Based on the criteria, TACAD incorporated specific components to: (a) respect cultural uniqueness; (b) understand cultural contexts; (c) use cultural examples; (d) have flexibility; (e) adopt multiple languages; (f) have culturally matched bilingual research team members; and (f) engage community consultants and research participants. Presentation styles were tailored to Asian culture. Through the process, both surface and in-depth cultural tailoring was done. TACAD used a free-form matrix information architecture and included menus based on the four components. *Graphic User Interface controls*,  the *Ruby on Rails (ROR)* framework, and the Xen hypervisor were used. Due to the use of ROR, different language versions could be easily added to the program, and cultural

tailoring methods used in this program could been easily adopted to different sub-ethnic groups. All the usages of different components will be automatically recorded in the server, which will allow the evaluation of different components. For instance, the usages of individual educational modules will be recorded on the server, so the association of the usages of specific modules to outcome variables could be easily determined later. To assess contamination, we will gauge crosstalk by open-ended questions about it at T1&2. We will estimate its effects statistically by testing if intervention effects are weaker among those who crosstalk.

[figure not shown]
Alzheimer's Association (AA) Website. The AA website has information in various areas related to AD and caregiving

For instance, the webpage on caregiving includes information on caregiving, care option, financial/legal planning, caregiver health, daily care, stages and behaviors, and safety. The content will be available in the three languages at the project website. The usages of the AA website and additional information searches (the participants will use them only through the project website) will be automatically recorded through the project server and later used for data analyses. Both groups will be asked to maintain their usual care. The interventionists will weekly remind the control group to use the AA website.

Instruments. The instruments to measure caregivers' health outcomes (primary outcomes; Hypothesis 1) include: (a) Multidimensional Caregiver Strain Index, Perceived Stress Scale, Acculturation Stress Scale (ASS), 148 and Social Readjustment Rating Scale (SRRS)  (to measure stress); (b) the Women's Symptom Index (to measure physical and psychological symptoms); and (c) EQ-5D-5L(to measure the quality of life). The instruments to measure care recipients' health outcomes (primary outcomes; Hypothesis 1) will include: (a) Informant Questionnaire on Cognitive Decline in the Elderly (IQCODE)(to measure the cognitive status of care recipients); (b) Lawton ADL/IADL Scale (to measure PLAD's activities of daily life); (c) Revised Memory and Behavior Problem Checklist (to measure behavioral and psychological symptoms of care recipients); (d) Neuropsychological Inventory Questionnaire (to measure care recipients' mood status); and (e) Quality of Life Scale in Alzheimer's Disease (to measure care recipients' quality of life). The instruments to measure caregiving experience (secondary outcomes; Hypothesis 2) will include: (a) Caregiver Activity Survey (to measure caregiving activity); (b) Ways of Coping Scale (to measure coping); (b) Pearlin Mastery, Loss, and Competence Scale (to measure caregivers' mastery of caregiving competence); and (c) Caregiver Assessment of Behavioral Skill Scale (to measure caregiving skills). 163 The theory-based variables (attitudes, self-efficacy, perceived barriers, & social influences; Hypothesis 3) will be measured using the modified Questions on Attitudes, Subjective Norm, Perceived Behavioral Control, and Behavioral Intention (QASPB). 164 Covariates that will be considered in determining the effect of TACAD on outcome variables include caregivers' sociodemographic characteristics and caregiving history (e.g., socioeconomic status, PLAD information, length of caregiving, co-residence with recipient). The reliability and validity of all the instruments have been established among Asian Americans. Cronbach's alpha of the instruments ranged from .70 to .96 among Asian Americans. Because no existing instruments have culture-specific measures, we will add open ended questions to all the measures to explore culture specific aspects that are missing in the specific measures. The same questionnaire will be used at the three time points except the questions on sociodemographic characteristics and caregiving history (e.g., socioeconomic status, PLAD information, length of caregiving, co-residence with recipient). The questions on sociodemographic characteristics and caregiving history (e.g., socioeconomic status, PLAD information, length of caregiving, co-residence with recipient) will be asked only at the pre-test. This has been clarified on p. 10.

The final versions of all materials will be uploaded via Modification for IRB review prior to any implementation. All communication/reminder templates will be uploaded via Modification prior to administration.

		SI	UBJECT POPULATIC	N	
	Protected Subject Polick on the check box (or double specifically studied for this research)	e clicl		le Doc	s) each population, if they are
	☐ Active Military Personnel		Children/Minors		Decisionally Impaired Adu
	☐ Emancipated Minors		Fetuses		Individuals with Limited English Proficiency
	☐ Neonates (Uncertain Viability)		Neonates (Non- Viable)		Prisoners
	☐ Pregnant Women		UT Staff/Employees		UT Students
	Research Participant	Info	rmation		
	5	cs. If y	you have multiple research pop	•	ncluding gender, health status, and one (e.g., teachers and students),
,	Asian American women who	are f	amily caregivers of persons l	living '	with Alzheimer's Disease
	Minimum Age				
	Include the minimum age range and students), clearly state the	-		ultiple	e research populations (e.g., teach
	18 years old				

